7.7.3. Hormonal Contraceptives

Pexidartinib has been indicated to be a moderate CYP3A4 inducer, as concurrent administration of pexidartinib decreased the AUC_{inf} of the CYP3A4 substrate midazolam by 57%. As the hormonal contraceptive ethinyl estradiol is a CYP3A4 substrate, there is a potential that exposure of ethinyl estradiol may decrease on concurrent administration with pexidartinib. As pexidartinib may cause embryo-fetal harm when administered to a pregnant woman, females of reproductive potential should be advised to use an effective, non-hormonal method of contraception during treatment with pexidartinib and for 1 month after the last dose. Males with female partners of reproductive potential should be advised to use an effective method of contraception during treatment with pexidartinib and for 1 month after the last dose. Female partners of male patients should concurrently use effective contraceptive methods (hormonal or non-hormonal).

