
Inclusion/ Exclusion Criteria:
	
To be eligible for enrollment, patient must meet all inclusion and exclusion criteria.
 
Inclusion Criteria:
 
 1. Age ≥18 years 2. Unresectable stage III or stage IV melanoma which is histologically confirmed at the treating institution with KIT mutation(s) not known to be resistant to PLX3397 (see Table 9-1). Note: Patients with KIT exon 8, 9, 11, 13, and 14 mutations are the most likely to be sensitive to PLX3397. Patients with KIT exon 17 or 18 mutations D816V, Y823D, and A829P should not be enrolled as they are not sensitive to PLX3397. Other KIT exon 17 or 18 mutations may be sensitive to PLX3397 and should be enrolled. 3. No limit on prior systemic therapies for melanoma. Patients who have not received prior therapy are eligible if they have a potentially sensitive KIT mutation. 4. Presence of measurable lesions by RECIST v1.1 5. ECOG performance status 0, 1, or 2 6. Life expectancy ≥3 months in the judgment of the investigator 7. Adequate organ and bone marrow function 
 a. Absolute neutrophil count (ANC) ≥1.5 X 10⁹/L, Hgb ≥10 g/dL, platelet count ≥100 X 10⁹/L b. AST/ALT ≤2.5 X upper limit of normal (ULN) or <5 X ULN in the presence of liver metastases, total bilirubin ≤1.5 ULN (unless due to Gilbert’s Syndrome, in which case it must be ≤2.5 mg/dL), albumin ≥3.0 g/dL c. Serum creatinine ≤1.5 X ULN or calculated creatinine clearance (CrCl) >60 mL/min using the Cockcroft-Gault formula 
Patients may be transfused or receive granulocyte-colony stimulating factor (G-CSF) or growth factors.
 8. Women of child-bearing potential must have a negative serum pregnancy test at Screening and must agree to use an effective form of contraception from the time of the negative pregnancy test up to 3 months after the last dose of study drug. Effective forms of contraception include abstinence, hormonal contraceptive (injectable or implantable) in conjunction with a barrier method, or a double barrier method. Women of non-child-bearing potential must have been postmenopausal for ≥1 year or surgically sterile. 9. Fertile men must agree to use an effective method of birth control during the study and for up to 3 months after the last dose of study drug. 10. Willingness and ability to provide written informed consent prior to any study-related procedures and to comply with all study requirements 
Exclusion Criteria:
 
 1. Prior treatment with a KIT inhibitor for melanoma 2. Known presence of NRAS or BRAF mutation

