3.3. Potential Risks and Benefits

The safety of pexidartinib has been evaluated in subjects with a range of tumor types, including solid tumors, hematologic malignancy, and in combination with chemotherapeutic agents. The selection of 1000 mg per day as the initial dose to be evaluated in the several studies was based upon the safety data from Study PLX108-01 and the safety of 1000 mg per day was further evaluated in several clinical studies.

In the GLP repeat-dose toxicology studies consisting of up to 13 weeks of pexidartinib dosing, test article-related AEs were noted in testes (testicular spermatogonia reduction), ovaries (ovarian follicular degeneration), liver, bone and bone marrow, hematology, and lymphoid changes; these changes are consistent with the pharmacological mechanism of action of pexidartinib. All test article-related findings were partially or fully reversible. Potential dose-related changes in bone marrow function can be monitored by peripheral blood cell count and differential counts. Because of the effects on reproductive organs, subjects will be monitored for changes in luteinizing hormone, follicle stimulating hormone, and other sex-specific hormone levels.

Effects on embryo fetal development have been observed in both rat and rabbit toxicology studies. Subjects in the study will be required to use adequate birth control during the study and for 90 days after the last dose of study drug administered.

Findings in the nonclinical canine safety pharmacology study suggest that pexidartinib may have a negative inotropic effect. Subjects will be monitored for changes in ejection fraction with cardiac echocardiograms.

In the clinical evaluation to date, among solid tumor patients, the most common AEs (occurring in $\geq 20\%$ of all patients treated with pexidartinib) observed have been fatigue, nausea, decreased

appetite, hair color change (depigmentation), vomiting, diarrhea, headache, and anemia. In the AML study, the most common AEs reported have been diarrhea, nausea, fatigue, febrile neutropenia, vomiting, decreased appetite, anemia, cough, hypokalemia, and increases in AST. In some instances, the increase in liver enzymes may require dose hold or modification. Dosing modification guidance is included within the protocol for AE monitoring. Liver function (serum chemistry), renal function (serum chemistry), and heart electrophysiology (QT interval corrected for heart rate [QTc] evaluation) will be monitored during this study.

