6.1. Inclusion Criteria

Each patient must meet all of the following inclusion criteria to be enrolled in the study to treatment:

1. Age ≥ 18 years
2. Unresectable stage III or stage IV melanoma which is histologically confirmed at the treating institution with KIT mutation(s) not known to be resistant to PLX3397.

Note: Patients with KIT exon 8, 9, 11, 13, and 14 mutations are the most likely to be sensitive to PLX3397. Patients with KIT exon 17 or 18 mutations D816V, Y823D, and A829P should not be enrolled as they are not sensitive to PLX3397. Other KIT exon 17 or 18 mutations may be sensitive to PLX3397 and should be enrolled.

3. No limit on prior systemic therapies for melanoma. Patients who have not received prior therapy are eligible if they have a potentially sensitive KIT mutation.
4. Presence of measurable lesions by RECIST v1.1
5. Eastern cooperative oncology group (ECOG) performance status 0, 1, or 2
6. Life expectancy ≥ 3 months in the judgment of the investigator
7. Adequate organ and bone marrow function
 - a. Absolute neutrophil count (ANC) $\geq 1.5 \times 10^9/L$, Hgb ≥ 10 g/dL, platelet count $\geq 100 \times 10^9/L$
 - b. AST/ALT $\leq 2.5 \times$ upper limit of normal (ULN) or $< 5 \times$ ULN in the presence of liver metastases, total bilirubin ≤ 1.5 ULN (unless due to Gilbert's Syndrome, in which case it must be ≤ 2.5 mg/dL), albumin ≥ 3.0 g/dL
 - c. Serum creatinine $\leq 1.5 \times$ ULN or calculated creatinine clearance (CrCl) > 60 mL/min using the Cockcroft-Gault formula

Patients may be transfused or receive granulocyte-colony stimulating factor (G-CSF) or growth factors.

8. Women of child-bearing potential must have a negative serum pregnancy test at Screening and must agree to use an effective form of contraception from the time of the negative pregnancy test up to 3 months after the last dose of study drug. Effective forms of contraception include abstinence, hormonal contraceptive (injectable or implantable) in conjunction with a barrier method, or a double barrier method. Women of non-child-bearing potential must have been postmenopausal for ≥ 1 year or surgically sterile.
9. Fertile men must agree to use an effective method of birth control during the study and for up to 3 months after the last dose of study drug.
10. Willingness and ability to provide written informed consent prior to any study-related procedures and to comply with all study requirements

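### Section 7.7.3 advises contraception for 1 month after the last dose, while Section 3.3 requires 90 days and inclusion criteria 8 and 9 up to 3 months

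*Combined protocol and SAP*

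**What the plan says.** Four parts of the current text bear on how long contraception should continue after the last dose.

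- **Section 7.7.3 (Hormonal Contraceptives).** The advice for women who could become pregnant is this: "use an effective, non-hormonal method of contraception during treatment with pexidartinib and for 1 month after the last dose". For men whose partner could become pregnant, the text is that they "should be advised to use an effective method of contraception during treatment with pexidartinib and for 1 month after the last dose". The section also says that the drug may cause embryo-fetal harm.
- **Section 6.1, inclusion criteria 8 and 9.** Women of child-bearing potential "must agree to use an effective form of contraception from the time of the negative pregnancy test up to 3 months after the last dose". For men, counted from the last dose: "Fertile men must agree to use an effective method of birth control during the study and for up to 3 months". The Synopsis repeats the period: "up to 3 months after the last dose of study drug".
- **Section 3.3 (Potential Risks and Benefits).** "Subjects in the study will be required to use adequate birth control during the study and for 90 days after the last dose". The sentence just before it gives the reason: "Effects on embryo fetal development have been observed in both rat and rabbit toxicology studies".
- **Section 14.4.** The sponsor must be notified of a pregnancy in a patient or a male patient's partner during treatment or within 3 months of stopping.

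On method, Section 7.7.3 advises women to use a non-hormonal one. Inclusion 8 counts as effective abstinence, "hormonal contraceptive (injectable or implantable) in conjunction with a barrier method, or a double barrier method".

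**The concern.** These sections serve one purpose, preventing pregnancy while the drug could still do harm, so they should give one duration. Section 7.7.3 gives the shortest and does not refer the reader to Section 6.1 or Section 3.3.

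The placement matters. Inclusion criteria are applied at entry, and Section 5.1 describes no further enrolment. For a patient already on treatment, the concomitant-medication guidance in Section 7.7 is a natural place for a site to look when advising at the end of dosing. A site that follows it literally would end contraception advice well before the period that Section 3.3 requires. What is at stake is participant safety. No estimate, error rate or decision rule is involved.

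**Working it through.** There is no plan figure to reproduce. The check sets the texts side by side, sizes the gap and counts who could be affected.

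**1. Durations and strength of wording**

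| Place | Applies to | Period after last dose | Wording |
|---|---|---|---|
| 7.7.3 | women and men | 1 month | advisory |
| 6.1 nos. 8 and 9, and Synopsis | women and men | up to 3 months | condition of entry |
| 3.3 | all subjects | 90 days | required |
| 14.4 | patients and partners | 3 months (notification) | required |

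Taken alone, the phrase in inclusions 8 and 9 could be read as a ceiling. Section 3.3 makes that reading hard to hold, because it states 90 days as a requirement. Section 14.4 agrees with 3 months. Section 7.7.3 is the outlier.

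**2. Size of the gap**

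Gap = required period minus advised period, with one month taken as 28 to 31 days:

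- 90 − 31 = 59 days
- 90 − 28 = 62 days

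The gap is about two months and is the same for both sexes.

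**3. Reach**

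- Section 5.1: 6 patients enrolled in the Pilot portion as of 30 June 2018, with 2 ongoing and re-consented into the extension. So 6 − 2 = 4 patients were no longer ongoing.
- Version 9.0 is dated 25 January 2020, which is 574 days after 30 June 2018. If the statement about ongoing patients instead refers to the version 8.0 date (11 September 2018), the interval is 501 days.
- Either interval is far longer than 90 days, so both the 1-month and the 3-month window had closed for those 4 patients before version 9.0 was issued.
- At most 2 patients remain. The documents do not give their sex or childbearing potential, or say whether they were still on drug in January 2020. Reach is therefore 0 to 2.

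**4. Which text is newer**

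The version 9.0 summary lists Section 7.7.3 among the updated sections and does not list Sections 3.3 or 6.1. That fits an update that was not carried through. It does not prove it, because the summary describes itself as top-line.

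**The case against.** The strongest reply is that the texts can be followed together. Section 7.7.3 is advisory and sits in a drug-interaction subsection, while Sections 3.3 and 6.1 are binding, and anyone who meets 3 months also meets 1 month. This is correct, and it is why 3 months is treated here as the operative period. It does not remove the problem, because a site reading Section 7.7.3 alone has no signal that a longer period applies. Section 14.4 offers only partial cover: it concerns reporting rather than prevention, and it also makes reporting voluntary after the follow-up visit or early termination.

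A second reply is that the newest text may state the sponsor's current position, so that 1 month is intended and 3 months is left over. The documents cannot settle this. It stands as a reason for the sponsor to confirm, but not as a reason to leave both periods in place.

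Two stronger readings are tempting and are not supported:

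- **That patients are being advised against what they agreed to at entry.** All 6 enrolled before versions 8.0 and 9.0. The version 7.0 summary says that inclusion 9 was revised without showing the older text, and the consent pages are not in the available copy. What these patients agreed to, at entry or at re-consent, cannot be read from the documents.
- **That inclusion 8 leaves a woman with only one working barrier.** Section 7.7.3 names ethinyl estradiol and says its exposure may decrease. It does not say that hormonal contraception has no effect, and the documents do not say whether injectable or implantable products contain that hormone. Only the difference in wording on method remains.

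**Conclusion.** The inconsistency is real and lies in current operative text. For both sexes, Section 7.7.3 states a period about two months shorter than the 90 days required in Section 3.3 and the 3 months in Sections 6.1 and 14.4. A secondary mismatch for women is that Section 7.7.3 advises a non-hormonal method while inclusion 8 still accepts a hormonal method with a barrier.

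Severity is minor. Reach is 0 to 2 extension patients, and sample size, endpoints and analysis are untouched. The conclusion assumes that the wording of Section 3.3 is binding and that 3 months and 90 days mean the same period. It does not assume that anyone was in fact advised wrongly, which the documents do not show.

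**What to change.** In Section 7.7.3, replace 1 month with 3 months (90 days) in the sentence for women and in the sentence for men. This keeps the stricter requirement. The sponsor should confirm the choice, because version 9.0 updated this section. Only if its safety data support 1 month should Sections 3.3, 6.1 and 14.4 and the Synopsis be changed to match instead.

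As a secondary edit, align the method wording of Section 7.7.3 and inclusion 8, including the Synopsis copy.

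The cost is two phrases for the main change and a short edit for the secondary one. Section 15.7 requires written ethics committee approval of a protocol change, and Section 15.8 requires re-approval of the subject information if that is revised. Both can go into the next amendment.

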7.7.4. Acid-reducing Agents

Avoid the concomitant use of proton pump inhibitors (PPIs) while taking pexidartinib. As an alternative to a PPI, administer pexidartinib 2 hours before or 2 hours after taking a locally-acting antacid, or if using a histamine 2 (H₂)-receptor antagonist, administer pexidartinib at least 2 hours before or 10 hours after taking an H₂-receptor antagonist.

7.8. Dosage Modification for Renal Impairment

The recommended dosage of pexidartinib for patients with mild to severe renal impairment (CL_{cr} 15 to 89 mL/min estimated by Cockcroft-Gault using actual body weight) is 200 mg in the morning and 400 mg in the evening.

7.9. Precautions and Restrictions

Because pexidartinib is a substrate for CYP3A4/5 and some fruits are CYP3A4/5 inhibitors, foods or beverages containing CYP3A4/5 inhibiting fruits (eg, grapefruit, pomelo, star fruit, and pomegranate) should be avoided throughout the study.

7.10. Management of Clinical Events

All necessary support care will be available to patients. For dose-modification guidelines, see Section 7.5.

7.11. Blinding and Unblinding

Blinding methods will not be employed; PLX3397 will be administered in open-label fashion.

7.12. Preparation, Reconstitution, and Dispensation

PLX3397 is an anticancer drug, and as with other potential toxic compounds, caution should be exercised when handling PLX3397 (see Section 7.14). Specific instructions on preparation, reconstitution, and dispensation will be provided in the PLX108-13 Pharmacy Manual.

7.13. Packaging and Labeling

PLX3397 capsules (200 mg strength) are manufactured, packaged, and labeled according to Good Manufacturing Practice (GMP) and GCP at the following address:

Catalent Pharma Solutions
[name]
[name]

7.14. Storage, Handling, and Accountability

PLX3397 capsules will be stored at the clinical site, as indicated on the study drug label, i.e., room temperature, between 15°–30°C (59°–86°F). Patients will be requested to store the study drug at the recommended storage conditions noted on the label, out of the reach of children or other cohabitants.

The Study drug provided in accordance with this Protocol will be kept in a secure place, and will only be supplied to Subjects participating in this Study. The Principal Investigator is accountable for all Study drug supplied by the Sponsor in accordance with this Protocol. In addition, the Principal Investigator must keep accurate and up-to-date dispensation records. Any Study drug accidentally or deliberately destroyed must be recorded in a timely fashion, including an explanation for the destruction in writing. Any discrepancies between the amounts of Study drug dispensed and returned must also be explained in writing. All such records of drug accountability must be entered on the corresponding Subject CRF's.

All unused and partially used Study drug must be returned to the designee as instructed by the Sponsor, or destroyed on Site in accordance with the established procedures for drug destruction, and with approval by the Principal Investigator or his/her designee. Details of destruction, including, but not limited to, the number of boxes destroyed, batch number, and the date and method of destruction must be recorded on the Study drug destruction logs.

7.15. Other Protocol-Specified Materials

There are no other supplies or materials required by the Protocol.

8.2. Arrangements for Recruitment of Subjects

Recruitment and enrollment strategies for this study may include recruitment from the investigator's local practice or referrals from other physicians. If advertisements become part of the recruitment strategy, they will be reviewed by IRB and/or IEC. Subjects will be compensated for their participation in this study.

8.3. Treatment Group Assignments

This is an open-label, sequential dose-escalation study with an expansion cohort. The initial dose level of PLX3397 will be 1000 mg/day administered BID. Thereafter, dose de-escalation will occur as described in Section 7.2.1. The expansion cohort will be enrolled at the RP2D according to inclusion and exclusion criteria (Section 6.1 and Section 6.2).

8.4. Withdrawal of Patients from Drug Treatment, Study and Patient Replacement

The Medical Monitor will monitor safety data throughout the course of the study. The Medical Monitor will review SAEs within timeframes mandated by company procedures and will review trends, laboratory data, and AEs at periodic intervals and provide for interim safety analyses if appropriate.

The reasons a patient may discontinue or be withdrawn from the study include, but are not limited to, AE, clinically significant disease progression, patient request, investigator decision,

protocol violation, patient noncompliance, and study termination by the Sponsor or IRB/IEC. When a patient discontinues or is withdrawn, the investigator will notify the Sponsor and should perform the procedures indicated in the End of Study column in the Schedule of Events within 28 days after discontinuation of study drug and before initiation of any new anti-cancer therapy. Follow-up information will be obtained for patients who discontinue their participation in or are withdrawn from the study.

Patients withdrawn from the study for reasons other than toxicity or clinically significant disease progression (e.g., protocol violation or noncompliance) may be replaced at the discretion of the medical monitor and the investigator. Study drug administration may be discontinued due to an AE or at the discretion of the investigator.

The consequence of withdrawal of consent by a patient will be that no new information will be collected from that patient and added to the existing data or any database. However, every effort will be made to follow all patients for safety.

8.5. Study Compliance

The study drug PLX3397 will be provided only to eligible patients under the supervision of the investigator or identified sub-investigator(s). The appropriate study personnel will maintain records of study drug receipt and dispensing. Any discrepancy regarding the dose administered and the reason for the discrepancy will be recorded in the eCRF. At each clinic visit, patients will be questioned about their compliance with study drug administration, and their dosing diary should be reviewed.

9.0 STUDY ASSESSMENT SCHEDULE

Event schedules are summarized in [Table 2-1](#) and [Table 2-2](#).

All patients must provide written informed consent. During the consent process, the person obtaining consent must inform the patient of all elements of the study. No protocol-specific procedures, including screening procedures, are to be performed until the patient has signed and dated an IRB/IEC-approved informed consent form. The study begins with the signing and dating of the informed consent form.

A patient will be considered enrolled in the study once all inclusion and exclusion criteria have been met, and the completed patient enrollment form has been submitted to the CRO, signed by the appropriate representative, and returned to the investigative site.

Screening procedures are to be performed within 28 days before C1D1 of study therapy.

The end of the study is defined as the date of the last dose of PLX3397 (see [Section 8.4](#) for reasons for discontinuation or withdrawal of a patient from the study).

9.1. Pilot Portion—All Cohorts

The schedule of events for patients in all cohorts in the Pilot portion is summarized in [Table 2-1](#) and detailed in the subsections below.

9.1.1. Screening Visit (Day –28 to Day –1)

- Informed consent
- Medical history
- Height and weight
- Complete physical examination
- Vital signs, including blood pressure, respiratory rate, pulse rate, and body temperature
- 12-lead ECG
- ECOG performance status evaluation
- Serum chemistry, including sodium, potassium, chloride, CO₂, calcium, phosphorus, glucose, blood urea nitrogen (BUN), creatinine, uric acid, total protein, albumin, total and direct bilirubin, AST, ALT, alkaline phosphatase, gamma glutamyl transferase (GGT), lactate dehydrogenase (LDH), and prothrombin time/international normalized ratio (PT/INR)
- Hematology: hemoglobin, hematocrit, white blood cell count with a differential, platelet count
- Urinalysis, including pH, protein/albumin, glucose, nitrites, ketones/acetone, and hemoglobin/blood
- Documentation of archival tissue availability
- KIT mutation documentation
- Computed Tomography (CT) chest, abdomen, and pelvis (PET/CT scan may be used as well)
- Adverse event assessment

